7. PLANNED ANALYSIS

This version of the TSAP describes analyses for HV and CF subjects.

Generally, HV and CF subjects will be evaluated separately. For safety analyses a total active treatment column will be displayed, if applicable.

The format of the listings and tables will follow the BI guideline "Reporting of clinical trials and project summaries" ([7](#)).

The individual values of all subjects will be listed, sorted by treatment group, subject number and visit (if visit is applicable in the respective listing). AE listings will be sorted by assigned treatment (see [Section 7.8.1](#) below for details). The listings will be contained in Appendix 16.2 (SDL) of the CTR.

Inferential statistical analyses of PK endpoints will be presented in Section 15.5 of the CTR and in Appendix 16.1.9.3.

Descriptive data analysis of PK endpoints will be presented in Section 15.6 of the CTR.

The following standard descriptive statistical parameters will be displayed in summary tables of continuous variables:

N	number of non-missing observations
Mean	arithmetic mean
SD	standard deviation
Min	minimum
Median	median
Max	maximum

For plasma concentrations as well as for all PK parameters, the following descriptive statistics will additionally be calculated:

CV	arithmetic coefficient of variation
gMean	geometric mean
gCV	geometric coefficient of variation

The data format for descriptive statistics of plasma concentrations will be identical with the data format of the respective concentrations. The descriptive statistics of PK parameters will be calculated using the individual values with the number of decimal places as provided by the evaluation program. Then the individual values as well as the descriptive statistics will be reported with three significant digits in the CTR.

Tabulations of frequencies for categorical data will include all possible categories and will display the number of observations in a category as well as the percentage (%) relative to the respective treatment group. Percentages will be rounded to one decimal place. The category missing will be displayed only if there are actually missing values. Percentages will be based on all subjects in the respective analysis set whether they have non-missing values or not.

7.1 DEMOGRAPHIC AND OTHER BASELINE CHARACTERISTICS

Only descriptive statistics are planned for this section of the report.

7.2 CONCOMITANT DISEASES AND MEDICATION

Concomitant diseases will be coded according to the most recent version of the Medical Dictionary for Regulatory Activities (MedDRA). Concomitant medication will be coded according to the most recent version of the World Health Organisation – Drug Dictionary.

Only frequency tables are planned for this section of the CTR.

A medication will be considered concomitant to a treatment, if

- it is ongoing at the time of administration of the respective treatment or
- it starts within the on-treatment phase of the respective treatment (see [Section 6.1](#)).

7.3 TREATMENT COMPLIANCE

Treatment compliance will not be analysed as a specific endpoint. Any deviations from complete intake will be addressed in the MQRM/BRPM (cf. [Section 6.2](#)) and described in the CTR.

7.4 PRIMARY ENDPOINT

Refer to [Section 7.8.1](#) for a description of the analysis of AEs, and in particular the analysis of the frequency of subjects with TEAEs, which is the primary endpoint of this trial.

7.5 SECONDARY ENDPOINTS

7.5.1 Key secondary endpoints

Not applicable.

7.5.2 Secondary endpoints

According to CTP Version 8.0 secondary endpoints are only defined for HV and not for CF subjects.

The analysis of secondary endpoints will be based on the PKS.

Dose proportionality of secondary endpoints (AUC_{0-12} , C_{max} , $AUC_{t,13}$, $C_{max,13}$ for HV) over the entire dose range will be evaluated as defined in the CTP, Section 7.3.2, by use of the power

model for healthy volunteers. For each of the secondary endpoints tables displaying geometric means of pairwise ratios together with 95% confidence intervals will be provided by dose group. A summary of results of the power model as described in the CTP, Section 7.3.2 will be displayed by a table. The relationship between the dose and the respective PK parameters will additionally be visualized graphically.

7.6.1 Safety endpoints

Further safety endpoints will be analysed as described in [Section 7.8](#) of this TSAP.

7.7 EXTENT OF EXPOSURE

Treatment exposure will be listed by means of the date and time of drug administration. Additionally, tables displaying descriptive statistics for treatment exposure (number of doses and total dose administered) will be given separately for HV and CF subjects.

7.8 SAFETY ANALYSIS

All safety analyses will be performed on the treated set.

7.8.1 Adverse events

AEs will be coded with the most recent version of MedDRA.

The analyses of AEs will be descriptive in nature. All analyses of AEs will be based on the number of subjects with AEs and not on the number of AEs.

For analysis, multiple AE occurrence data on the electronic case report form (eCRF) will be collapsed into one event provided that all of the following applies:

- All AE attributes are identical (lower level term, intensity, action taken, therapy required, seriousness, reason for seriousness, relationship, outcome, AE of special interest (AESI))
- The occurrences were time-overlapping or time-adjacent (time-adjacency of two occurrences is given if the second occurrence started at most 1 hour after the first occurrence ended)

For further details on summarization of AE data, please refer to 'Handling and summarization of adverse event data for clinical trial reports and integrated summaries' ([5](#)) and "Handling of missing and incomplete AE dates" ([3](#)).

The analysis of AEs will be based on the concept of treatment emergent AEs, i.e. all AEs will be assigned to the treatment phase, screening phase or follow-up phase as defined in [Section 6.1](#).

An overall summary of AEs will be presented. This overall summary will comprise summary statistics for the class of other significant AEs according to ICH E3 and for the class of adverse events of special interest (AESI). For the definition of AESI please refer to Section 5.3.10.1 of the CTP.

The frequency of subjects with AEs will be summarised by treatment (dose), primary system organ class and preferred term. AEs which were considered by the investigator to be drug related will be summarised separately. Separate tables will also be provided for subjects with serious AEs (SAEs), subjects with AESIs and subjects with other significant AEs (according to ICH E3). AEs will also be summarized by maximum intensity.

The system organ classes will be sorted according to the standard sort order specified by the European Medicines Agency (EMA), preferred terms will be sorted by total frequency (within system organ class).

A further table will present AEs by preferred term, dose group and intensity, sorted by descending relative frequency in any dose group.

For disclosure of AE data on ClinicalTrials.gov, the frequency of subjects with non-serious AEs occurring with an incidence of greater than 5 % (in preferred terms) will be summarised by treatment, primary system organ class and preferred term. The frequency of subjects with SAEs will also be summarised.

For disclosure of AE data in the European union drug regulating authorities clinical trials (EudraCT) register, the frequency of AEs, the frequency of non-serious AEs with an incidence of greater than 5 % (in preferred terms) and the frequency of SAEs will be summarised.

Tables prepared for public disclosure (ClinicalTrial.gov and EudraCT) will include subjects of both trial parts combined (HV and CF subjects).

7.8.2 Laboratory data

The analyses of laboratory data will be descriptive in nature and will be based on BI standards (6). If possible, analyses for HV will be based on original values. If multiple reference ranges apply for one parameter (e.g. due to different age groups) for HV, analyses will be based on normalised values, which means transforming to a standard unit and a standard reference range. Analyses for CF subjects will be based on normalized values. If references ranges are not available, analyses will be based on original values.

Laboratory data will be analysed both quantitatively as well as qualitatively. The latter will be done over comparing laboratory data to their reference ranges. Values outside the reference range will be highlighted in the listings.

Dose groups will be compared with descriptive statistics of laboratory values over time and by analysing differences from baseline (see [Section 6.7](#) for definition of baseline).

Additionally, frequency tables of changes between baseline and last values on treatment with respect to the reference ranges will be presented. For electrolytes, descriptive statistics of values over time and differences from baseline will be provided comparing all active doses versus placebo for HV. Furthermore graphical representations over time will be generated for serum electrolytes for HV and CF subjects and for urine electrolytes for HV subjects.

Clinically relevant findings in laboratory data will be reported as AEs and will be analysed as part of AE analysis.

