6) ECGs will be recorded for a 10-sec duration after the subjects have rested for at least 5 min in a supine position. Screening ECG can be performed with site ECG equipment but transferred to

7) All pre-dose measurements to be completed prior to dosing. Drug inhalation will take place at the same clock time, for morning and evening dosing, throughout the investigational period. Dosing will be under supervision at the trial site for all days.

8) Serum electrolyte samples only to be collected on Day 1, 2, 3, 4, 5, 6, 7, 8, 16, 23, 30 using local laboratory values in addition to central laboratory values.

9) End-of-study visit ; Including physical examination, weight, pregnancy test, review of vital signs/ECG/laboratory, serum pregnancy test (WOCBP only) at the end-of-study examination.

11) AEs and concomitant therapies will be recorded throughout the trial but will be specifically asked for at the time points indicated in the [Flow Chart](#) above

12) Systolic and diastolic blood pressures (BP) as well as pulse rate (PR) will be measured by a blood pressure monitor at the times indicated in the Flow Chart, after subjects have rested for at least 5 min in a supine position

13) If several actions are indicated at the same time point, the intake of fluid/meals will be the last action.

14) The time is approximate; the respective procedure is to be performed and completed within 3 h prior to drug administration. Allocation to treatment may be performed at any time following enrolment but must be completed prior to first drug administration.

15) Urine pregnancy test for females (WOCBP only) on Day 1 and Day 7. Serum pregnancy test at screening, Day-5 to -3, and e.o.s. visit.

16) All ECGs on Day 1, Day 2, Day 7 & Day 8 will be in triplicate. All other ECGs to be single.

17) Body Plethysmography / Pulmonary function to be performed using Investigative site spirometry equipment.

18) On Day 7 for dose group 400 μ g and 1200 μ g only, for each PK timepoint, both a PK sample and a metabolite identification (MIST) sample will be taken (refer to [Section 5.4.2.2](#)).

19) Urine drug screen and alcohol breath test to be performed at screening and Pre-dose Day 1.

FLOW CHART II – CF SUBJECTS

| | | Period | | | | | | | | | | | | | |
|---|-----|--------|------------------------|--|--------|--|---|---|------------------------|-------------------|-----------------------|--------------------------------|-----------------|---------------------|-----------------|

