- 13) Unsupervised Pulmonary Function (FEV₁, PEF) with AM3® device
- 14) Phone call to be made twice a day, ideally at the time of study drug administration ([see section 5.3.6](#)). During the afternoon or evening calls, AEs should be collected in line with a morning call
- 15) Allocation to treatment may be performed at any time following enrolment but must be completed prior to first drug administration. Randomisation not required for CF subjects undergoing second treatment period
- 16) AEs and concomitant therapies will be recorded throughout the trial, but will be specifically asked for at the time points indicated in the [Flow Chart II](#) above including during phone calls when patients are ex clinic.
- 17) Respimat device and AM3® device training initially, then instruction (if required).
- 18) Systolic and diastolic blood pressures (BP) as well as pulse rate (PR) will be measured by a blood pressure monitor at the times indicated in the Flow Chart II, after subjects have rested for at least 5 min in a supine position.
- 19) Includes, urine pregnancy test for females at Screening, Day 1, Day 7, Day 14 and Day 30. Serum pregnancy test at Day -5 to -3, and e.o.s. visit.
- 20) To be measured on home based spirometer (AM3®), prior to drug administration.
- 21) Baseline ECG (Day 1) must be in triplicate. All other ECGs to be single.
- 22) Urine drug screen and alcohol breath test to be performed at both screening and Pre-dose Day 1.,
- 24) Serum electrolytes to be collected using local laboratory values in addition to central laboratory values.
- 25) Planned time is required for technical reasons and the actual dates and times could be between Day -7 to -3.

TABLE OF CONTENTS

| | |
|---|-----------|
| CLINICAL TRIAL PROTOCOL..... | 1 |
| TITLE PAGE | 1 |
| CLINICAL TRIAL PROTOCOL SYNOPSIS | 2 |
| FLOW CHART I – HEALTHY VOLUNTEERS | 5 |
| FLOW CHART II – CF SUBJECTS..... | 8 |
| TABLE OF CONTENTS | 11 |
| ABBREVIATIONS..... | 15 |
| 1. INTRODUCTION..... | 17 |
| 1.1 MEDICAL BACKGROUND | 17 |
| 1.2 DRUG PROFILE | 18 |
| 1.2.1 Nonclinical pharmacology..... | 18 |
| 1.2.2 Safety pharmacology..... | 19 |
| 1.2.3 Toxicology | 19 |
| 1.2.5 Drug product | 20 |
| 1.2.6 Clinical studies and experience in humans | 20 |
| 2. RATIONALE, OBJECTIVES, AND BENEFIT - RISK ASSESSMENT | 22 |
| 2.1 RATIONALE FOR PERFORMING THE TRIAL | 22 |
| 2.2 TRIAL OBJECTIVES..... | 22 |
| 2.3 BENEFIT - RISK ASSESSMENT..... | 22 |
| 2.3.1 Procedure-related risks | 23 |

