Fertility has not been assessed in nonclinical species, but no adverse effects have been observed on reproductive organs in 4-week toxicity studies in rats and dogs, suggesting that there is a low risk to fertility. At the time this current study is planned to start, embryo-fetal development studies of BI 443651 will not have been conducted. Therefore only female subjects of child bearing potential willing to accept highly effective methods of contraception [See exclusion criteria [section 3.3.3](#) for definition of highly effective methods of contraception] through the duration of this study and for 30 days after will be included, otherwise only males, and females of non-child bearing potential and non-lactating women will be included in this study.

The nonclinical safety studies (safety pharmacology and pivotal toxicity studies) to support the clinical study 1363.2 are described and referred to in the Investigator's Brochure for BI 443651 in Cystic Fibrosis and COPD. These studies have been conducted in compliance with Good Laboratory Practice and have been carried out in an OECD country.

The only exception is the study on the effects of BI 443651 on the hERG (human ether-a-go-go related gene)-mediated potassium current [[n00248843](#)]. This study was performed in an OECD country but without formal adherence to the principles of GLP (non-GLP). Data quality and integrity of the study however are given as study reconstruction is ensured through adequate documentation of the study conduct and archiving of data. Therefore the validity of the study is considered not compromised by its non-GLP status and as such there is no impact on the evaluation of the respective endpoints of this safety pharmacology study.

Whilst not all safety effects may be predicted, based on mechanism and systemic toxicological finding the only potential systemic toxicity is changes in serum electrolytes and particularly increases in serum potassium. These changes are easily monitored and treatable if observed. The following safety measures will be applied in this study in order to minimize the risk for the healthy volunteers and CF subjects:

- Frequent safety laboratory testing will be performed with a focus on electrolytes (see [Flow Chart I](#) & [Flow Chart II](#)). Dose escalation will be stopped as soon as at least 2 subjects at one dose level within one population type on active drug showed serum potassium levels ≥ 5.5 mmol/L in non-haemolysed blood

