11. Any laboratory value outside the reference range that the investigator considers to be of clinical relevance, specifically volunteers with serum potassium > upper limit of normal should be excluded; Safety laboratory screening and Day -7 to Day -3, evaluation can be repeated twice during screening.
12. For healthy volunteers, repeated measurement (i.e. > 2 measurements) of systolic blood pressure outside the range of 90 to 140 mmHg, diastolic blood pressure outside the range of 50 to 90 mmHg. Volunteers will be excluded with a pulse rate outside the range of 45 to 90 bpm.
13. A marked baseline prolongation of mean QT/QTcF interval (such as QTcF intervals that are repeatedly greater than 450 ms in males or repeatedly greater than 470 ms in females) or any other relevant ECG finding at screening or prior to randomisation (see section [5.3.8](#)).
14. A history of additional risk factors for Torsades de Pointes (such as heart failure, hypokalemia, or family history of Long QT Syndrome).
15. Within 10 days prior to administration of trial medication, use of drugs that might reasonably influence the results of the trial or that might prolong the QT/QTcF interval
16. Intake of drugs with a long half-life (more than 24hrs) within 30 days or less than 10 half-lives of the respective drug prior to administration of trial medication **unless this is allowed medications as indicated in [Table 4.2.2.1:1](#)**.
17. CF subjects treated with non-permitted concomitant medication. Specifically medications causing changes in serum potassium are restricted (please refer to Table 4.2.2.1:1)
18. Current or previous participation in another interventional trial, including where an investigational drug has been or will be administered within 60 days or 5 half-lives (whichever is longer) prior to screening.
19. For healthy volunteers and CF subjects: current smokers or ex-smokers of less than 12 months and/or with a pack year history of more than 5 years.
20. Positive test for alcohol or drugs, at screening or pre-dose on Day 1 prior to randomization. (Unless this can be explained by the subject's medication).
21. Drug or alcohol abuse or any condition that, in the investigator's opinion, makes them an unreliable study subject or unlikely to complete the trial. Consumption of 20 g/day (2 units of alcohol) in females, or 30 g/day (3 units of alcohol) in males.

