4.2.2.3 Restrictions on diet and life style

Diet and lifestyle restrictions before and after administration of trial medication:

While admitted to the trial site the subjects are restricted from consuming any other foods or drinks than those provided by the staff. Standardised meals will be served at the time points described in [Flow Chart I](#) & [Flow Chart II](#).

Day 1, Day 7 and Day 14

While admitted to site on Day 1, Day 7 and Day 14, from 1 hour before drug intake until lunch, water intake and meals are restricted as per [Flow Chart I](#) & [Flow Chart II](#). From lunch onwards (on Day 1, Day 7 and Day 14), for healthy volunteers only, water intake must be up to an additional 750 mL (maximum 1,500 mL) until 1 hour prior to the evening drug administration.

The total amount of liquid intake will be documented.

For all subjects while in the unit, standardised meals will be served at the time points described in respective flowcharts. A snack is allowed (if completed) 1 hour prior to the morning dose, or started 30 minutes after the evening dose, post-body plethysmography (healthy volunteers only), if required. Use of additional table salt is not allowed during in-house confinement at the trial site.

On all other days (excl. Day 1, Day 7 and Day 14), no time restrictions will occur to meals outside of 07:00 to 20:00.

Grapefruits, Seville oranges and their juices should be avoided 7 days before and until the last PK timepoint. Excess of dried fruits (defined at > 1 standard adult portion per day) and dietary supplements containing high level of sodium and potassium should also be avoided during the trial. All non-prescribed supplements should be avoided.

For HV subject alcoholic beverages are not permitted from 48 hours prior to:

- screening
- study drug administration at Day 1, until after safety laboratory tests at Day 12.
- end of study visit

For CF subjects excess of alcoholic beverages are not permitted 48 hours prior to:

- screening
- each treatment period (Visit 2 & 3) at Day 1, until after safety laboratory tests at Day 14.
- end of study visit

Intake of methylxanthine-containing drinks or foods (coffee*, tea, cola*, energy drinks*, chocolate, etc.) are not allowed during in-house confinement and 8 hours prior to the morning of in-clinic appointments with pulmonary function tests.

*Decaffeinated beverages are allowed.

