5.3.2 Safety endpoints

The following endpoints are further safety criteria of interest:

- Related AEs (including clinically relevant findings from the physical examination)
- Safety laboratory tests
- 12-lead ECG
- Vital signs (blood pressure, pulse rate)
- Pulmonary function tests (FEV₁, FVC, FEV₁/FVC ratio (CF subjects only), FEF₂₅₋₇₅)

12-lead ECG endpoints

For the definition of baseline and a summary of time points please refer to [Section 6.7](#).

Quantitative ECG endpoints:

The following quantitative ECG endpoints will be determined for the ECG variables RR, PR, QRS, QT, HR, QTcF and QTcB derived as described in [Section 9.1](#):

- absolute values (per time point)
- changes from baseline (per time point)
- percent changes from baseline (per time point; only for HR, PR, QRS)

Categorical ECG endpoints

The following categorical ECG endpoints will be determined based on the quantitative ECG endpoints:

- New onset (meaning that this or a higher category was not present at baseline) of maximum QTcF interval > 450 to 480 msec, > 480 to 500 msec, or > 500 msec on treatment. For assignment of a particular subject to one of the above categories, all time points on-treatment will be considered. If baseline is missing, but the maximum absolute QT(c) interval falls in a category other than normal (i.e. when QTcF > 450 msec), then this is categorized as a new onset in the respective category. If baseline is missing, but the maximum absolute QT(c) interval is normal, then it is categorized as 'No new onset'.
- Maximum change from baseline in QT interval of ≤ 60 msec, or > 60 msec on treatment
- Maximum change from baseline in QTcF interval of ≤ 30 msec, > 30 to ≤ 60 msec, or > 60 msec on treatment

The occurrence of any of the following will be viewed as "notable findings":

- New onset (not present at baseline) of uncorrected QT interval > 500 msec at any time on treatment
If baseline is missing, any occurrence of QT interval > 500 msec at any time on treatment will be a notable finding
- New onset of QTcF interval > 500 msec at any time on treatment
If baseline is missing, any occurrence of QTcF interval > 500 msec at any time on treatment will be a notable finding
- Increase in QTcF interval from baseline by > 60 msec at any time on treatment

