6. GENERAL ANALYSIS DEFINITIONS

6.1 TREATMENTS

For basic study information on treatments to be administered please refer to Section 4 of the CTP.

The trial is composed of two parts, a multiple rising-dose (MRD) and a cross-over part. Both parts are randomised, placebo-controlled and double-blind.

During the MRD part, healthy volunteers (40 subjects planned to be included) will be treated with doses of 100, 400, 1200 and 1800 µg b.i.d. of BI 443651 or placebo.

For the cross-over part, a total of 24 subjects with CF will be included in the study. Each subject will receive both placebo and active drug at the dose level 600 µg b.i.d. of BI 443651.

Measurements (such as ECG, spirometry, vital signs, or laboratory parameters) or adverse events (AE) will be assigned to treatments and study periods by applying the following rules:

- **Screening:** measurements made or AEs which started prior to first administration of trial medication.
- **On-treatment:** measurements made or AEs which started between first administration of trial medication in a treatment period and first administration of trial medication in the next treatment period or end of REP will be assigned to the preceding treatment. The REP for BI 433651 is defined as 30 days after the last trial medication application.
- **Follow-up:** measurements made or AEs which started between the end of REP and first administration of trial medication in the next treatment period or trial termination date. In case of 2 or more treatments, the follow-up will be summarized according to the previous treatment.

Table 6.1: 1 Flow chart of analysis phases for adverse events, laboratory tests, vital signs and spirometry for healthy volunteers

Study analysis phase	Start	End
Screening	Date of informed consent	Date/time of first device actuation for administration of BI 443651 or placebo
On treatment	Date/time of first device actuation for administration of BI 443651 or placebo	0:00 AM on day after end of REP or 0:00 AM on day after trial termination date Whatever comes first
Follow-up (not identical to time points acc. To CTP)	0:00 AM on day after end of REP	trial completion date

Table 6.1: 2 Flow chart of analysis phases for adverse events, laboratory tests, vital signs, ECG and spirometry for CF subjects

Study analysis phase*	Start	End
Screening	Date of informed consent	Date/time of first device actuation for administration of BI 443651 or placebo (first treatment period)

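### Unless an unseen sponsor standard narrows the window, the laboratory shift table classifies an off-drug electrolyte sample (normally Day 30 in healthy volunteers), so a potassium rise that resolves reads as no shift

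*SAP*

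**What the plan says.** SAP 7.8.2 plans by-time descriptive statistics and changes from baseline, graphs of serum electrolytes, and highlighting of out-of-range values in listings. In addition, "frequency tables of changes between baseline and last values on treatment with respect to the reference ranges will be presented". It names no other per-subject categorical laboratory table, gives no window of its own, and refers to a sponsor laboratory standard (SAP reference 6).

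SAP 6.1 sets the window. Table 6.1: 1 covers laboratory tests in healthy volunteers and closes the on-treatment phase after the REP or at trial termination, whichever is first. "The REP for BI 433651 is defined as 30 days after the last trial medication application". Table 6.1: 2 does the same for CF subjects, with an extra cut at the first dose of the next period. Its footnote sends period 2 measurements that fall in the period 1 phase to the blinded report planning meeting.

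On sampling, Flow Chart I footnote 8 reads "Serum electrolyte samples only to be collected on Day 1, 2, 3, 4, 5, 6, 7, 8, 16, 23, 30", and the full panel is repeated at end of study (Days 37 to 44). For CF subjects, Flow Chart II footnote 19, attached to safety laboratory entries, reads "Includes, urine pregnancy test for females at Screening, Day 1, Day 7, Day 14 and Day 30". Protocol 4.2.2.3 sets an alcohol restriction "until after safety laboratory tests at Day 14".

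For QTcF categories the SAP takes a different approach (5.3.2): "For assignment of a particular subject to one of the above categories, all time points on-treatment will be considered".

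**The concern.** Protocol 2.3.2 states that "the only potential systemic toxicity is changes in serum electrolytes and particularly increases in serum potassium". A shift table is the natural place to see how many subjects moved out of range on each treatment. For potassium it can inform almost only through its post-baseline class, because exclusion criterion 11 says "specifically volunteers with serum potassium > upper limit of normal should be excluded", so subjects are expected to start in range or low.

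If the post-baseline class comes from a sample taken weeks after dosing, the table describes recovery rather than exposure. The subjects of most interest are also the likeliest to look unchanged, because protocol 6.2.3 has clinically relevant abnormal values followed until they are acceptable again and sends early stoppers through follow-up. A reader could take a column of normal-to-normal entries as evidence that potassium did not move during dosing, which the table cannot show.

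**Working it through.** **Healthy volunteers.** The inputs are the last dose on Day 7 (protocol 4.1.4), the 30-day REP (SAP 6.1) and the draws in Flow Chart I footnote 8.

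- End of REP for a completer: 7 + 30 = Day 37.
- Post-baseline electrolyte draws in the window: Days 2 to 8 (7 draws, the last about 24 h after the final dose) and Days 16, 23 and 30 (3 draws), so 10 in all, or 11 if end of study is held on Day 37.
- Classified sample: Day 30, which is 30 − 7 = 23 days off drug. With end of study on Day 37 it is 37 − 7 = 30 days.
- Early stoppers, last dose on Day d = 1 to 6: the REP ends on Day d + 30 = 31 to 36, so Day 30 is always inside. The gap is 30 − d = 29 to 24 days, provided follow-up is attended.
- Draws from Days 2 to 8 that are classified when a Day 30 sample exists: 0 of 7.

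Illustration with assumed counts: if 2 of 8 active subjects in a dose group go above range during dosing and are normal by Day 30, the planned table shows 0/8 and a dosing-phase worst-value table shows 2/8 (25%).

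Other HV laboratory tests are largely unaffected, because their last full panel before end of study is pre-dose on Day 7.

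**CF subjects.** The laboratory columns of Flow Chart II are broken, so a Day 30 draw is inferred from the in-clinic visit and footnote 19. Washout W is counted in days from the last dose to Day 1 of period 2.

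- Day 30 visit: 30 − 14 = 16 days off drug. With the visit windows (Day 14 −1/+3, Day 30 ±5) the range is 25 − 17 = 8 to 35 − 13 = 22 days.
- Period 1, short washout: the period 2 Day −7 to −3 sample lies W − 7 to W − 3 days after the last dose. It is inside the period 1 REP whenever W is 30 to 33 (33 − 3 = 30) and can be up to W = 37 (37 − 7 = 30). At W = 30 the Day 1 pre-dose sample is inside too. Read literally, one of these then replaces Day 30, subject to the blinded report planning meeting. From W = 38 to the 6-week maximum, Day 30 is last.
- Period 2: an end-of-study sample (Days 44 to 51) counts if taken no later than last dose + 30. That is Day 44 for a last dose on Day 14 (gap 30), or Days 44 to 47 for a last dose on Day 17 (gaps 27 to 30).

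In each of these cases the classified sample is off drug and neither dosing-phase sample (Days 7 and 14) is used.

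**Chance flags under a worst-value table.** The plan gives no per-sample false-flag rate p, so it is assumed. For k independent samples, P(at least one flag) = 1 − (1 − p)^k.

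| p | HV, k = 7 | expected among 8 pooled HV placebo | CF, k = 2 |
|---|---|---|---|
| 1% | 6.8% | 0.54 | 2.0% |
| 2.5% | 16.2% | 1.30 | 4.9% |
| 5% | 30.2% | 2.41 | 9.8% |

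For comparison, the last-value rule at 2.5% gives 8 × 0.025 = 0.20 HV placebo subjects. In CF the expected counts among 24 per treatment are 24 × 0.049 = 1.2 against 24 × 0.025 = 0.6. Within-subject correlation lowers the HV figure: at 2.5% and assumed correlations of 0.3, 0.5 and 0.7 it is 13.7%, 11.5% and 8.9%.

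**The case against.** The case against changing anything is substantial.

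- The sponsor laboratory standard may define the last on-treatment value more narrowly, and protocol 7.3.4 allows further analysis intervals. This stands, and the point is conditional on it. On the text available, SAP 6.1 governs.
- The table is a supplement. Clinically relevant rises are reported and analysed as adverse events, and by-time summaries include the maximum, which with 8 active subjects per dose group would expose a single high value. This stands and limits the harm. It does not make the table informative about dosing.
- No decision rests on the table. Escalation goes through safety review of the accumulating data, stopping criteria act on individual values, and no confirmatory hypothesis is tested. This stands.
- The HV analysis was specified before the interim lock, a repeat is not planned (protocol 7.4.1), and protocol 2.3.2 already reports no relevant electrolyte effects with dosing up to 1800 µg b.i.d. over 6.5 days. An HV table can therefore only be a labelled post-hoc addition. The SAP revision describing the CF analyses precedes final database lock.
- The CF reading rests on a broken flow chart. This stands, and it is given only as inference.

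A reader might infer that a potassium signal would vanish from the report, or that the SAP drops the count of subjects with abnormal values planned in protocol 7.3.4. Neither is supported. The other displays remain, and SAP 7.8.2 does not repeat that count but does not withdraw it.

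**Conclusion.** The point holds for HV serum electrolytes as written, conditional on the unseen standard: the shift table normally classifies a sample 23 days off drug (24 to 29 for early stoppers who attend follow-up, 30 if end of study falls on Day 37) and uses none of the seven samples from Days 2 to 8. For CF subjects the same conclusion is probable but inferred, and which off-drug sample is classified depends on the washout, the visit windows and the planning meeting. It would be too strong to say that it is always Day 30.

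The consequence is one potentially misleading table about the protocol's main systemic risk, with the underlying values visible elsewhere. This is a cheap improvement of minor to moderate importance. The day counts assume that scheduled follow-up samples are taken; where every later sample is missing, a dosing-phase value would be classified.

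**What to change.** In SAP 7.8.2, for serum electrolytes:

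1. Add one shift table by treatment on the worst central-laboratory value (highest for potassium), from first dose through Day 8 in healthy volunteers and through the Day 14 visit in each CF period. Flag haemolysed samples where that is recorded.
2. Label the existing table as showing the last value up to the end of the REP.
3. Mark the added HV table as post hoc.

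Keep the 30-day REP for adverse events.

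The cost is a few lines of SAP text and one table from central data already collected. The documents do not say whether haemolysis reaches the database; if it does not, a footnote is needed. The main downside is the extra chance flags calculated above, which the placebo column displays. The table would also not reproduce the potassium stopping-rule count, because protocol 5.3.7 bases dosing decisions on local values that are not entered in the database; a footnote should say so.
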